**Notes:**

- In patients with thyroid and other head and neck cancers, imaging of the relevant areas (e.g., neck, skull base) is required at baseline; other areas of scanning may differ depending on disease type. See the separate Imaging Manual that will be distributed to the sites for details.
- Additional scans can be performed as needed to evaluate potential sites of disease.
- Disease assessments will utilize RECIST 1.1 or RANO as appropriate to tumor type (refer to Section 7.8.1).
- Guidelines on the technical parameters of how scans should be performed will be provided in the Imaging Manual
- Concomitant, ongoing medications plus those administered within 14 days prior to the planned start of treatment.

## 7.2 Cycle 1

The procedures listed below will be performed at the indicated intervals. Observations, routine laboratory tests, and HRQoL assessments will be performed prior to selpercatinib dosing on that day unless otherwise indicated. Routine clinic visits and C1D1 evaluations performed within  $\pm 2$  days of the nominal visit day will not be considered protocol deviations, with the exception of ECGs and PK, which must be performed relative to the dose of selpercatinib on that day as indicated below.

Laboratory values on C1D1 pre-dose must meet the inclusion/exclusion criteria for treatment to proceed.

### Day 1

- Symptom-directed physical examination, weight, and ECOG or Lansky score.
- Vital signs.
- Resting 12-lead ECG: pre-dose (up to 4 hours pre-dose).
- Serum or urine pregnancy test for women of childbearing potential (surgically sterilized females or those who have not experienced menses for at least 2 years are not required to be tested).
- Hematology (as described in Section 7.1).
- Serum chemistries (as described in Section 7.1).
- Liver function tests (as described in Section 7.1).
- Calcitonin, CEA: for patients with MTC only. For each patient, all tests for calcitonin and CEA should be performed in the same laboratory to minimize intra-patient, lab-to-lab variability in their measurement.
- Thyroglobulin: for patients with non-MTC thyroid cancer only (unless not measurable due to presence of anti-thyroglobulin antibodies). For each patient, all tests for thyroglobulin should be performed in the same laboratory to minimize intra-patient, lab-to-lab variability in their measurement.
- Serum cortisol, serum ACTH, 24-hour urine for free cortisol: optional for patients with Cushing's disease related to their cancer. If done, urine collection should begin pre-dose.
- Whole blood for cfDNA analysis: obtained prior to treatment on C1D1.
- Selpercatinib administration.
- Outpatient diaries for recording daily selpercatinib dosing, H2 blockers, and antacids.
- AEs.
- Concomitant medications.
- Patient-reported outcomes to be completed pre-dose:
  - For MTC patients with diarrhea present at baseline: bowel diary.

- For patients 18 years or older: European Organization for Research and Treatment of Cancer Quality of Life Questionnaire-Core 30 (EORTC QLQ-C30).
- For patients age 13 to 17 years: Pediatric Quality of Life Inventory-Core Module (PedsQL) for teens.
- For patients age 12 years: PedsQL for children.

#### Day 8

- Symptom-directed physical examination, weight, and ECOG or Lansky score.
- Vital signs.
- Resting 12-lead ECG: 2 hours post-dose ( $\pm 10$  minutes) and prior to PK blood draw at this time point. Further ECGs may be required based upon results of the 2 hours post-dose ECG (refer to [Table 7-1](#), footnote “j” for specific instruction based upon QTcF value observed).
- Blood sample for PK (2 mL whole blood): pre-dose (within 1 hour prior to dosing), and post-dose at 1, 2 and 4 hours ( $\pm 15$  minutes) and 8 hours ( $\pm 30$  minutes).
- Selpercatinib administration.
- Outpatient diaries for recording daily selpercatinib dosing, H2 blockers, and antacids.
- AEs.
- Concomitant medications.
- For MTC patients with diarrhea present at baseline: bowel diary.

#### Day 15

- Symptom-directed physical examination, weight, and ECOG or Lansky score.
- Vital signs.
- Hematology (as described in [Section 7.1](#)).
- Serum chemistries (as described in [Section 7.1](#)).
- LFTs (as described in [Section 7.1](#)).
- Thyroid panel, including TSH, free T3, and free T4.
- Urinalysis.
- Calcitonin, CEA: for patients with MTC only. For each patient, all tests for calcitonin and CEA should be performed in the same laboratory to minimize intra-patient, lab-to-lab variability in their measurement.
- Thyroglobulin: for patients with non-MTC thyroid cancer only (unless not measurable due to presence of anti-thyroglobulin antibodies). For each patient, all tests for thyroglobulin should be performed in the same laboratory to minimize intra-patient, lab-to-lab variability in their measurement.
- Serum cortisol, serum ACTH, 24-hour urine for free cortisol: optional for patients with Cushing’s disease related to their cancer. If done, urine collection should begin pre-dose.

- Whole blood for cfDNA analysis.
- Selpercatinib administration.
- Outpatient diaries for recording daily selpercatinib dosing, H2 blockers, and antacids.
- AEs.
- Concomitant medications.
- For MTC patients with diarrhea present at baseline: bowel diary.

### Day 22

Telephone contact for safety: The site will contact the patient by telephone to assess for selpercatinib tolerability, continuation of study drug, and whether the patient needs to return to the clinic earlier than planned. If not tolerating the drug well, the patient should be seen at least every 14 days to assess AEs, and the patient should be contacted regularly to assess AE status. The patients should be reminded to complete the bowel diary for the previous week and bring the diary to the C2D1 visit.

## **7.3 Cycles 2 and Higher**

The following procedures will be performed prior to dosing as noted. Routine clinic visits performed within  $\pm 3$  days of the nominal visit day will not be considered protocol deviations.

- Symptom-directed physical examination, weight, and ECOG or Lansky score: Day 1 of each cycle starting with C2. Beyond Cycle 7, physical examination is only required when the patient returns to the clinic for disease assessment cycles (C7, C9, C11, and C13, then every 12 weeks [Q12W] thereafter).
- Vital signs: Day 1 of each cycle starting with C2. Beyond Cycle 7, vital signs are only required when the patient returns to the clinic for disease assessment cycles (C7, C9, C11, and C13, then Q12W thereafter).
- Resting 12-lead ECG (2 hours post-dose on C2D1, C3D1, C4D1, C5D1 and C6D1 [ $\pm 10$  minutes]) and subsequently in alignment with required disease assessment timepoints (C7, C9, C11, and C13, then Q12W thereafter through Cycle 26). Further ECGs may be required based upon results of the 2 hours post-dose ECG (refer to [Table 7-1, footnote “j”](#) for specific instruction based upon QTcF value observed). Additional ECGs may be performed if clinically indicated.
- Serum or urine pregnancy test for women of childbearing potential (surgically sterilized females or those who have not experienced menses for at least 2 years are not required to be tested): Day 1 of each cycle starting with C2. For Cycle 7 and beyond, patients may have serum or urine pregnancy test completed at local healthcare facilities during non-disease assessment cycles.
- Hematology (as described in [Section 7.1](#)): Day 1 of each cycle starting with C2. For Cycle 7 and beyond, patients may have hematology completed at local healthcare facilities during non-disease assessment cycles.

**Note:** Patients found to have treatment-emergent hematologic toxicity of Grades 3 or 4 will be monitored at least weekly until resolution.

- Serum chemistries (as described in Section 7.1): Day 1 of each cycle starting with C2. For Cycle 7 and beyond, patients may have serum chemistries completed at local healthcare facilities during non-disease assessment cycles.

**Note:** Patients found to have treatment-emergent laboratory toxicity of Grades 3 or 4 will be monitored at least weekly until resolution.

- LFTs (as described in Section 7.1): C2D1, C2D15, C3D1, C3D15, and D1 of each cycle starting with C4. For Cycle 7 and beyond, patients may have LFTs completed at local healthcare facilities during non-disease assessment cycles.

**Note:** Patients found to have treatment-emergent laboratory toxicity of Grades 3 or 4 will be monitored at least weekly until resolution.

- Thyroid panel: C3D1 and then  $\pm 7$  days of each radiologic disease assessment.
- Urinalysis: Beyond C1D15, urinalysis is only required when clinically indicated.
- Calcitonin, CEA: for patients with MTC only; should be measured C2D1 and then  $\pm 7$  days of each radiologic disease assessment. For each patient, all tests for calcitonin and CEA should be performed in the same laboratory to minimize intra-patient, lab-to-lab variability in their measurement.
- Thyroglobulin: for patients with non-MTC thyroid cancer only (unless not measurable due to presence of anti-thyroglobulin antibodies); should be measured C2D1 and then  $\pm 7$  days of each radiologic disease assessment. For each patient, all tests for thyroglobulin should be performed in the same laboratory to minimize intra-patient, lab-to-lab variability in their measurement.
- Serum cortisol, serum ACTH, 24-hour urine for free cortisol: for patients with Cushing's disease related to their cancer; should be measured C2D1 and then  $\pm 7$  days of each radiologic disease assessment. If done, urine collection should begin pre-dose.
- Participants under age 18 who have not yet obtained full adult height should undergo radiograph of one knee every 6 months for growth plate assessment. Image the same knee that was imaged at baseline.
- Whole blood for cfDNA analysis: C2D1 only
- Radiographic disease assessment: every 8 weeks ( $\pm 7$  days) beginning with C3D1 through C13D1 and every 12 weeks ( $\pm 7$  days) thereafter until PD, withdrawal of consent, or initiation of a new anticancer therapy(ies), including imaging of the chest, abdomen, and pelvis, utilizing the same modality(ies) as used for the baseline imaging assessment. Additionally, any studies performed at baseline that are positive for sites of disease should be repeated at all post baseline assessments. Additional studies can also be performed as clinically indicated. Please see the Imaging Manual for guidelines on how the various imaging studies should be performed.

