- v. Baseline disease assessment with radiographic tumor measurements using CT or MRI of chest, abdomen, and pelvis or any other areas with suspected disease involvement within 28 days of C1D1. During Phase 2, brain imaging is required at baseline for all RET fusion-positive patients, patients with a history of CNS metastases, or other patients if clinically indicated and subsequent serial scans if brain metastases are present at baseline (MRI preferred, CT with contrast is acceptable if MRI contraindicated). For each modality, IV and oral contrast should be utilized (chest CT does not require IV contrast) unless there is a clear contraindication (e.g., decreased renal function or allergy that cannot be addressed with standard prophylactic treatments). In the absence of known or suspected disease involvement, head and neck CT/MRI scans are not required for malignancies other than those originating in the head and neck region. Other areas of scanning may also differ depending on disease type. Post-baseline scans should be performed every 8 weeks ( $\pm 7$  days) for one year and every 12 weeks ( $\pm 7$  days) thereafter, including imaging of the chest, abdomen, and pelvis, using the same modality(ies) as used for baseline imaging assessment until PD, withdrawal of consent, or initiation of a new anticancer therapy(ies). Additionally, any studies performed at baseline that are positive for sites of disease should be repeated at all post-baseline assessments. Additional studies can also be performed as clinically indicated. In addition, Investigators may conduct an initial tumor evaluation on C2D1 ( $\pm 7$  days) and a confirmatory tumor evaluation a minimum of 4 weeks (i.e., 28 days) after the first tumor evaluation that shows a CR or PR by RECIST 1.1 (or RANO, as appropriate to tumor type), if consistent with local regulatory authority requirements. In addition, an initial post baseline assessment on C2D1 ( $\pm 7$  days) is encouraged if consistent with regulatory guidelines. If a scan is performed on C2D1, the next scan should continue according to the schedule above (beginning at C3D1). All scans will be collected and stored at a central facility to permit central reviewer assessment if desired. Please see the Site Imaging Manual for guidelines on how the various imaging studies should be performed.
- w. If not performed within the last 8 weeks.

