## **7.8 Procedures for Special Tests**

### **7.8.1 Tumor Measurements**

Tumors will be assessed by the Investigator according to the guidelines provided in Section 7 and the Imaging Manual. Investigators should use the same method consistently for an individual patient throughout the study. Assessments of both measurable and non-measurable disease will be made by the Investigator using RECIST 1.1 (refer to [Appendix G](#)) or RANO criteria ([Appendix H](#)) as appropriate to tumor type; or a comparable assessment method depending on location of tumor.

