### **7.8.2 Central Collection of Radiographic Studies**

Baseline screening radiographic studies and all subsequent radiographic studies and their associated reports will be collected and stored for future independent radiological review.

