1.1. Objectives and Endpoints

Objectives	Endpoints
Primary	

 Assess the antitumor activity of selpercatinib in patients with Advanced Solid Tumors, including RET fusion-positive solid tumors, medullary thyroid cancer, and other tumors with RET activation 	
 ORR based on IRC assessment using RECIST 1.1
Secondary	

 Assess the antitumor activity of selpercatinib in patients with Advanced Solid Tumors, including RET fusion-positive solid tumors, medullary thyroid cancer, and other tumors with RET activation 	
 ORR based on investigator assessment using RECIST 1.1 CNS ORR (by IRC; patients with RET fusion NSCLC and brain metastases) CNS DOR (by IRC; patients with RET fusion NSCLC and brain metastases) Biochemical response TTR (by IRC and investigator) TTBR (by IRC and investigator) DOR (by IRC and investigator) CBR (by IRC and investigator) PFS (by IRC and investigator) OS

 Determine the safety profile and tolerability of selpercatinib in patients with Advanced Solid Tumors, including RET fusion-positive solid tumors, medullary thyroid cancer, and other tumors with RET activation 	
 Safety per CTCAE (including but not limited to): frequency and severity of TEAEs, SAEs, deaths, and clinical laboratory abnormalities Changes in haematology and blood chemistry values Assessments of physical examinations Vital signs, and ECGs

 To characterize the PK properties of selpercatinib 	
 Plasma concentrations of selpercatinib and PK parameters, including, but not limited to, AUC_{0-24}, C_{max}, and T_{max}

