4.2. Participant Dispositions

A detailed description of participant disposition will be provided, according to Consolidated Standards of Reporting Trials publishing requirements, including a summary of the number and percentage of participants entered the study, enrolled in the study, and treated, as well as number and percentage of participants completing the study or discontinuing prior to study completion (overall and by reason for discontinuation).

The disposition of patients will be summarized by tabulating the number and percentage of patients as of a data cutoff date:

- treatment disposition
 - starting dose of selpercatinib and frequency of administration
 - continuing to receive selpercatinib, and
 - permanently discontinued selpercatinib and the primary reason
- study disposition
 - patients who discontinued from study and the primary reason, and
 - time on study.

Patients with PD may be allowed to continue study drug if, in the opinion of the investigator, the patient is deriving clinical benefit from continuing study treatment, and continuation of treatment is approved by the sponsor. The number and percentage of such patients continuing to receive study drug after the documentation of disease progression will be presented.

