4.3.2. ORR by Investigator Assessment

Best overall response for each patient based on the RECIST 1.1 by investigator assessment will be analyzed as a secondary endpoint analysis. ORR by investigator will be analyzed in the same manner as ORR by IRC.

To evaluate agreement between IRC and investigator assessments, 2×2 contingency table will be prepared. Correspondence rate and its 2-sided 95% exact binomial CI will be estimated.

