4.3.3. Duration of Response

DOR will be calculated for patients with CR or PR as their best overall response. For such patients, DOR is defined as the number of months from the start date of CR or PR (whichever response status is observed first) and subsequently confirmed, to the first date that recurrent or disease progression is objectively documented. If a patient dies (irrespective of cause) without documentation of recurrent or PD beforehand, then the date of death will be used to denote the response end date.

DOR will be right censored for patients who meet one or more of the following conditions:

- subsequent anticancer therapy or cancer-related surgery in the absence of documented disease progression
- died or experienced documented disease progression after missing 2 or more consecutively scheduled disease assessment visits
- alive and without documented disease progression on or before the data cutoff date, and
- discontinue treatment and loss to follow up.

If a patient meets more than one of these conditions, then the scenario that occurs first will be used for the analysis. The event or censoring date will be determined based on the conventions listed in [Table JZLA.4.1](#).

Table JZLA.4.1. DOR Censoring Scheme

Situation	Date of Event or Censoring	Outcome
Death or disease progression between planned disease assessments	Date of death or first disease assessment showing disease progression, whichever occurs first	Event
Subsequent anticancer treatment started before disease progression or death (without disease progression beforehand)	Date of last evaluable disease assessment prior to start of subsequent anticancer treatment	Censored
Death or disease progression after missing 2 or more consecutively scheduled disease assessments	Date of last evaluable disease assessment visit without documentation of disease progression before the first missed visit	Censored
Alive and without disease progression	Date of last evaluable disease assessment	Censored
Discontinue treatment and loss to follow up	Date of last evaluable disease assessment	Censored

Abbreviation: DOR = duration of response.

The patient's overall response status as of the date cutoff date will be summarized by tabulating the number and percentage of patients with confirmed CR or PR as follows:

- response continuing
- subsequent anticancer therapy/cancer-related surgery without documented disease progression beforehand
- discontinued treatment and loss to follow up

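### IRC duration of response and PFS are usually censored at an investigator PD that the IRC does not share, and no planned output counts these patients; for DOR and CNS DOR a count line and one sensitivity analysis would close the gap (minor).

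*Protocol*

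**What the plan says.** **When scans stop.** Protocol Section 7.3 runs scheduled imaging "thereafter until PD, withdrawal of consent, or initiation of a new anticancer therapy(ies". Table 7-1 footnote v has the same stop: "using the same modality(ies) as used for baseline imaging assessment until PD, withdrawal of consent, or initiation of a new anticancer therapy(ies". Appendix G repeats it. Section 3.1 limits disease assessments in long-term follow-up to patients without PD. None of these places says whose PD is meant.

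**Who reads.** Section 7.8.1 states "Tumors will be assessed by the Investigator according to the guidelines provided in Section 7". Under Section 7.8.2 the scans are "collected and stored for future independent radiological review". No step is described in which the IRC confirms PD before scanning or treatment stops.

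**How the endpoints are censored.** SAP Tables JZLA.4.1 (DOR) and JZLA.4.2 (PFS) censor at the last evaluable assessment a patient who is alive without PD, who starts new anticancer therapy first, or who stops treatment and is lost. Death or PD after two or more missed scheduled assessments is censored at "Date of last evaluable disease assessment visit without documentation of disease progression before the first missed visit". Death or PD between planned assessments is an event.

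**Planned outputs nearby.**
- SAP 1.1 lists "PFS (by IRC and investigator") and likewise DOR by both assessors.
- SAP 4.2 tabulates the primary reason for stopping selpercatinib, and the number of "such patients continuing to receive study drug after the documentation of disease progression will be presented".
- SAP 4.3.2 plans a two-by-two table "To evaluate agreement between IRC and investigator assessments", in the section on ORR.
- SAP 4.3.3 tabulates the status of responders at the cutoff: response continuing, new therapy or surgery without prior PD, off treatment and lost, PD, or died.
- SAP 4.3.4 has CNS DOR assessed by the IRC alone.

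**The concern.** An investigator PD ends the scan schedule, is a reason to stop treatment (Protocol Section 6.4), and opens the way to new systemic therapy, which Section 6.3.3 bars before documented PD. If the IRC later sees no PD on the same scans, the patient leaves the IRC risk set at about the time the treating physician judged the disease to be worsening. Kaplan-Meier estimation treats that patient as having the same outlook as those who remain. If the outlook is in fact worse, the censoring is informative and IRC DOR and PFS come out too favourable.

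At stake is how far a reader can trust the IRC durability figures. DOR is the weaker case. Investigator DOR is computed among investigator responders with the investigator's own start dates, so it does not show what happens to IRC responders when the unshared PD is handled differently. CNS DOR lacks even that comparison. In the status table, an IRC responder with an unshared investigator PD, no new therapy and no loss to follow-up has no category and could be counted as *response continuing*.

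**Working it through.** **No figure to reproduce.** The documents give no power or precision statement for PFS or DOR. They also give no rate of disagreement on PD, no extent of scanning after PD, and no survival after PD. The sizes below are therefore illustrations under stated assumptions.

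**Step 1. Is censoring the usual outcome?** Without new therapy or a later scan, the main escape from censoring is death before two assessments are missed. Two intervals are 16 or 24 weeks, that is 16 × 7 / 30.4375 = 3.68 months or 5.52 months. With exponential survival after PD of median m months, P(death in window) = 1 − 0.5^(window/m):

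| m (months, assumed) | 16 weeks | 24 weeks |
|---|---|---|
| 3 | 57% | 72% |
| 6 | 35% | 47% |
| 12 | 19% | 27% |
| 24 | 10% | 15% |

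Censoring is the more common outcome unless survival after PD is very short. New therapy moves further patients to censoring.

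**Step 2. How large could the effect be?** Simulation of PFS, 300,000 patients per case.
- From the protocol: scans every 8 weeks to week 48 (C13D1), then every 12 weeks.
- Assumed: exponential investigator PFS, median 18 months; cutoff at 48 months; median 12 months from investigator PD to death.
- Assumed shares: d of investigator PDs are not shared by the IRC; f of these would show IRC PD at the next scan, and the rest carry the ordinary IRC hazard; c are still scanned after investigator PD; nt of those no longer scanned start new therapy.
- Reading A censors a death after two missed scans. Reading B counts it as an event.

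Check on the set-up: the last scan before 24 months is at week 96, or 22.08 months, so investigator PFS at 24 months should be 0.5^(22.08/18) = 42.7%. The simulation gives 42.7%.

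Overstatement of 24-month IRC PFS against full IRC follow-up, in percentage points (A / B):

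| Case | d = 0.1 | d = 0.2 | d = 0.3 |
|---|---|---|---|
| f = 0.5, c = 0.5, nt = 0 | 0.9 / 0.7 | 1.8 / 1.3 | 2.7 / 2.0 |
| f = 0.5, c = 0.5, nt = 0.5 | 1.1 / 1.0 | 2.2 / 2.0 | 3.4 / 3.0 |
| f = 0.5, c = 0, nt = 0 | 1.8 / 1.4 | 3.7 / 2.7 | 5.7 / 4.0 |
| f = 1, c = 0, nt = 0 | 2.6 / 2.2 | 5.4 / 4.4 | 8.3 / 6.6 |

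With f = 0, c = 0 and no deaths, where discordance is unrelated to IRC risk, the differences are 0.0, 0.1 and −0.1: no bias. With c = 0.8, d = 0.2, f = 0.5 and nt = 0.5, the overstatement is about 0.9 / 0.8. The rows with c = 0 are extremes.

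**Step 3. What do the planned outputs already show?** For d = 0.2, f = 0.5, c = 0.5, nt = 0.5, the 24-month rates are:
- investigator PFS: 42.7%
- composite (investigator PD counted as an event where the IRC has none and scanning ended): 44.0%
- IRC PFS with full follow-up: 45.4%
- planned IRC PFS: 47.6% (A) or 47.4% (B)

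Planned investigator and IRC PFS bracket the full-follow-up value. When all scanning ends, the composite agrees with investigator PFS within 1 point.

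**Step 4. DOR status table.** If the same model is carried over to responders, those with an unshared PD, scans ended, no new therapy and alive at the cutoff make up 0.5%, 1.0% and 1.5% for d = 0.1, 0.2 and 0.3 (c = 0.5, nt = 0.5). With c = 0 and nt = 0 the shares are 2.0%, 4.0% and 5.9%.

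**The case against.** **Investigator PFS is already planned.** This stands. It counts the unshared PD as an event, and Step 3 shows that a PFS composite adds little. The discontinuation reasons in SAP 4.2 help too. The bracket is approximate, though: it holds because the model mostly puts the IRC's PD later than the investigator's. A reader might infer that nothing planned bears on the question; for PFS the documents do not support that. For DOR and CNS DOR the gap remains.

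**Scanning often continues.** Protocol Section 6.4 allows treatment beyond PD and foresees a subsequent progression, and Section 7.5 asks for an end-of-treatment scan if none is recent. This stands, and it is why the cases with continued scanning are the better guide.

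**The status label is undefined.** The SAP does not define *response continuing*, does not say the table is for the IRC only, and has a separate line for patients off treatment and lost. A reader might infer that these responders will be reported as continuing; the text shows only that they could be.

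**Other documents may settle it.** The IRC charter and Imaging Manual are not available here and could address reading order or imaging after PD. That the investigator's PD stops the scans is an inference from Sections 7.8.1 and 7.8.2, though no other mechanism is described.

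**Stopping scans at local PD is common practice.** Agreed; no extra scans are proposed. SAP 4.1 permits further exploratory analyses, but pre-specifies none on this point.

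**Conclusion.** The point holds as a minor one. IRC DOR and PFS are usually censored at an investigator PD that the IRC does not share, and no planned output separates these patients. The direction is upward only if they are nearer to IRC PD or death than others at risk. The size is unknown and could be zero. With half of the discordant patients near IRC PD, half still scanned and 10% to 30% discordance, it is roughly 1 to 3 points at 24 months, and every one of those inputs is assumed.

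Two stronger readings are not supported. A reader might infer that the durability results are known to be inflated, but the documents contain no discordance data. A reader might also infer that the main result is at risk. The primary endpoint, IRC ORR, is a proportion and does not pass through this censoring, and PFS and DOR are secondary, single-arm and descriptive.

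What remains is specific: IRC DOR has no comparison in its own responders, CNS DOR has none at all, and the status table has no line for these patients.

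**What to change.** 1. In SAP 4.3.3, add a status-table line for IRC responders censored after an investigator PD that the IRC did not share. Give the same count for CNS DOR (4.3.4) and for PFS (4.3.9).
2. In SAP 4.3.3, pre-specify one sensitivity analysis of DOR among IRC responders in which an unshared investigator PD is an event when scanning ended. For PFS this is optional, because it would be close to the planned investigator PFS.
3. As a clarification only, state whether assessments no longer required after investigator PD count as missed scheduled ones. In the scenarios run with no later scans and no new therapy, over median survival after PD of 6 to 24 months, this choice moved the 24-month rate by 0.1 to 2.7 points.

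**Cost.** A little more analysis work, from data already collected and with no new patient procedures. The supportive DOR estimate may be less favourable and may overcorrect: in the PFS example of Step 3 the composite is 44.0% against 45.4% with full follow-up, 1.4 points too low. It should be read beside the planned estimate, not in its place.
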